serological criteria, will be recruited for this study. 42 will undergo oral immunotherapy, while 42 will be followed as natural history controls but will be offered similar therapy, should it be successful, at the completion of one year. OIT subjects will initiate therapy with a 2-day rush desensitization treatment using oral doses of milk, in our Clinical Investigation Unit. They will then continue the highest tolerated dose of milk at home for two weeks. Subsequently, they will return for weekly increases in doses until a maximum of 200 ml of milk is ingested daily. The primary clinical outcome will be a comparison of the amount of milk consumed safely on oral challenge performed prior to OIT, when the OIT dose has reached its maximum (200 ml or highest tolerated dose) and after one year of therapy. Patients will also be followed with clinical symptom scores and adverse event diaries and we will monitor immunological parameters such as changes in milk-specific IgE, blocking antibodies (IgG4 and IgA) and regulatory T and B cells. We expect that we will be able to see important improvement in the ability to safely ingest milk and other dairy products, and this will be accompanied by significant decreases in IgE and increases in Regulatory T and B cells.

BACKGROUND INFORMATION:

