Withdrawal from therapy: Subjects will be carefully monitored during the in hospital rush therapy phase, as well as during the home OIT phase. Instructions for treatment of reactions will be provided as above. Patients who are enrolled will be informed that in previously published studies, minor allergic reactions are common in these protocols (mild itching, abdominal discomfort) but resolve with increased time on therapy. Subjects will be withdrawn if they cannot tolerate the low dose, rush desensitization phase, if they have more than 2 or more moderate or severe reactions during the home (maintenance) OIT phase, if they experience a rare or unforeseen complication such as severe flares of eczema or chronic gastrointestinal symptoms (e.g. development of eosinophilic esophagitis) and if the parents or subjects wish to voluntarily terminate therapy.

3.3.6 : Variables measured. The following variables will be measured in each patient:

A. The primary outcome measure will be the presence of desensitization defined by the ability to tolerate 200 ml of milk 1 year after the start of the trial. This is a qualitative variable with three categories: total desensitization (200 mL of cow's milk); partial desensitization (20–200 mL); and failed desensitization (<20 mL milk). Only patients presenting total desensitization were regarded as being successfully desensitized.

B. Secondary outcome measures will be:

1. Number and severity of adverse reactions occurring after oral exposure to milk during the desensitization and follow-up phases.
2. Minimum dose of milk that triggered symptoms during the desensitization protocols or challenge tests.
3. Days until desensitization was achieved.
4. Indices of desensitization :
 - a. Change in skin prick test weal size, comparing tape transferred, cpoputor measured diameters and areas of the skin tests to milk extract.
 - b. Levels of sIgE, sIgA and sIgG4 before desensitization, during follow-up and at the end of the study.
 - c. T and B reg before desensitization, during follow-up and at the end of the study.

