4.0. Statistical Considerations

A: Sample Size calculation: Given that previous studies have attributed at least 50% improvement in the ability to tolerate milk(24) with an α of 0.05 and a power (1- β) of 0.80, a sample of 42 cases and 42 controls will be recruited.

B: Statistical Analysis: Statistical analyses will be performed using paired t-tests. A p value of <0.05 will be considered significant. Descriptive statistics of the variables including means, standard deviations and frequencies were computed for all study variables. The concentrations of milk –specific IgE, IgG and IgA, the size of the skin tests , T reg and Breg expression at the different study time-points will be compared with their baseline values using the one-sample paired t-test and to the control using a 2 sample t-test .

Multiple regression models will be used to assess factors associated with response to desensitization, including baseline demographic characteristics; gender; age; baseline SPT and specific IgE, Treg and Breg numbers, and vitamin D level.

5. Ethical Considerations

In the consent form given at study enrolment, participants will be advised that they will be randomly assigned to either oral immunotherapy or observation for a one year period. Participants will also be advised that their data will be shared only among the OIT study team. Participants in the observation control group who will not receive OIT treatment, will be told that they may to undergo such therapy after a year of observation and a positive oral food challenge.

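### The protocol states two non-equivalent primary outcomes, milk volume at three OIT milestones and 200 ml tolerance at one year, and does not say which governs.

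*Combined protocol and SAP*

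**What the plan says.** The Experimental Approach summary gives this definition: "The primary clinical outcome will be a comparison of the amount of milk consumed safely on oral challenge performed prior to OIT". The same sentence goes on to name two later occasions for the comparison: "when the OIT dose has reached its maximum (200 ml or highest tolerated dose) and after one year of therapy". The variable is a volume, observed on three occasions, each tied to a stage of OIT.

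Section 3.3.6 A gives another definition: "The primary outcome measure will be the presence of desensitization defined by the ability to tolerate 200 ml of milk". The assessment is placed one year from trial start. The section describes this as a three-level variable (total at 200 mL, partial from 20 to 200 mL, failed below 20 mL) and adds: "Only patients presenting total desensitization were regarded as being successfully desensitized".

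Section 4.0 B does not mention either outcome by name. It opens with "Statistical analyses will be performed using paired t-tests" and sets a threshold of p<0.05. Its comparison "to the control using a 2 sample t-test" is listed for antibodies, skin tests, Treg and Breg. Challenge volume and 200 ml success are not in that list, and no test for a categorical or binary outcome is named. Multiple regression is reserved for factors associated with response.

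**The concern.** A trial's headline claim is whatever its primary outcome shows. Here two definitions both carry that label, and they differ in scale, number of assessments and clock. Without a ranking, an author could report either as the primary result, and the 5% error rate attaches to neither in particular.

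The two also differ in how well they isolate the effect of OIT. Section 3.2 excludes children whose entry challenge is negative, so everyone enrolled starts as a reactor. The Control Subjects paragraph of section 3.3.4 foresees controls who become tolerant without treatment. If the volume outcome is analysed as change from a child's own baseline, natural resolution counts as benefit. A comparison of the randomized arms does not have that weakness.

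**Working it through.** **Step 1. The definitions side by side**

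| Feature | Experimental Approach | Section 3.3.6 A |
|---|---|---|
| Variable | Volume tolerated on challenge | Three categories; success means total |
| Assessments | Three | One |
| Clock | Before OIT, maximum dose, one year of therapy | One year after trial start |
| Comparison | Over OIT milestones; no control arm named | Measured in each patient; arms not named |

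**Step 2. Does the sample size show which was meant?** Section 4.0 A gives 42 per arm for at least a 50% improvement in the ability to tolerate milk, with alpha 0.05 and power 0.80. It gives no control rate and no SD, so 42 cannot be rebuilt from the stated inputs. Three readings, two-sided, with z = 1.960 and 0.842:

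- Difference of 50 percentage points: n = [1.960·√(2p̄q̄) + 0.842·√(p₁q₁ + p₂q₂)]² / 0.5², which gives 11 to 15 per arm depending on the control rate.
- Between-arm mean difference of 0.5 SD: n = 2·(2.802/0.5)² = 62.8, so 63 per arm.
- Within-arm paired change of 0.5 SD: n = (2.802/0.5)² = 31.4, so 32.

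A 42 appears only with added assumptions, for example 60% versus 30%. The sample size therefore does not identify the outcome.

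**Step 3. Error rate with two unranked primaries.** Independent tests at 0.05 give 1 − 0.95² = 0.0975; the Bonferroni bound is 0.10. Counting the two post-baseline volume comparisons separately gives 1 − 0.95³ = 0.1426. These figures take each test to be valid for the effect of OIT.

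**Step 4. How the two versions behave when OIT does nothing.** The section 3.2 doses accumulate to 0.1, 0.4, 1.4, 4.4, 14.4, 44.4, 89.4 and 149.4 mL. Assumptions, none from the documents: geometric mean threshold 10 mL, log10 SD 0.7, retest noise 0 to 0.3 log10, and resolvers scored 200 mL. Children who pass every step at entry are excluded. The paired t-test uses 42 OIT children; the between-arm Fisher test uses 42 per arm.

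| Assumed one-year resolution | Paired test on volume shows improvement |
|---|---|
| 0% | 0–5% |
| 2% | 1–11% |
| 5% | 16–27% |
| 10% | 62–64% |
| 15% | 88% |

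Ranges run over the retest noise, and repeat runs move them by a few points. On the log scale the figures are lower: 7–14% at 5% resolution and 31–45% at 10%. The Fisher test on 200 ml success is significant in about 3% of runs or fewer.

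A second model gives the same pattern. It uses standardized thresholds, within-patient correlation 0.6 and a success cut at +1 SD. With no natural improvement the paired test is significant in 4.8%, Fisher in 2.3%, and at least one in 7.0%. With natural improvement of 0.25 SD the paired test reaches 41%, and with 0.5 SD 95%. Fisher stays below 3%.

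**The case against.** The best defence is that section 3.3.6, under Research Methods, is the only formal list of outcomes, while the other sentence sits in a narrative summary. The categories are cut-points of tolerated volume, and one year of therapy nearly coincides with one year from trial start. On that reading 3.3.6 A simply makes the summary operational. This is a good reason to keep 3.3.6 A, but it does not remove the conflict. The protocol has no precedence rule, and section 4.0 B leads with a test suited to the volume version and names none for a category.

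The second objection stands: neither place states the comparison. The summary does not call its analysis within-patient, and 3.3.6 A does not say OIT versus control. The before-after reading is inferred from the milestones and the paired t-tests.

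The third also stands. The simulation measures the bias of an uncontrolled comparison, which would remain if the volume outcome were the only primary. The cost of having two primaries is the error rate in step 3.

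A reader might go further and infer that the sponsor means to pick the outcome after seeing the data. The documents show only that the choice is left open. Nor do they support reading 62–88% as the false-positive rate to expect. They give no annual resolution rate for challenge-positive patients aged 6 to 20, and at zero resolution the rate is 0–5%.

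**Conclusion.** The contradiction is established by the text alone: two primary outcomes that are not equivalent, with no hierarchy. Its direct statistical cost is a familywise error of up to about 0.0975 if both are tested at 0.05 and are independent. Because one outcome is a cut of the other's scale, they are likely to be positively related, which would put the true figure lower.

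The further risk is conditional. If the volume version is analysed before-after in the OIT arm, it can be significant with no OIT effect. How often depends almost wholly on the assumed resolution rate, from no inflation at zero to well over half of runs at 10%. The between-arm 200 ml comparison is not affected in this way, so the two versions can lead to different conclusions from the same trial. The 42 per arm is not shown to be wrong; it only fails to settle which outcome it serves.

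**What to change.** In both the Experimental Approach and section 3.3.6 A, name one primary outcome: the proportion with total desensitization at one year, OIT versus control as randomized. Section 4.0 B should name a test for two proportions. Make change in tolerated volume from the entry challenge, compared between arms, a secondary outcome. State that only the 3.3.6 A outcome carries the confirmatory claim, and restate the sample size for it. With 42 per arm, 80% power and two-sided 0.05, the detectable absolute difference is about 0.17 to 0.30 for assumed control success of 0% to 30%.

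The volume change loses its primary status. The change also goes beyond wording, because these places must be reconciled on how and when 200 ml tolerance is assessed in both arms:

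- Section 3.2: the standard challenge stops at 150 ml, below the 200 ml success threshold.
- Section 3.3.3: a 300 ml challenge follows one month at 200 ml, and a 12-month challenge is given only for those tolerating less than 200 ml.
- Section 3.3.4, Control Subjects: skin tests, blood tests and diaries are listed, but no challenge.
- Section 5: a positive challenge after a year appears only as a condition for controls to receive OIT.
- Appendix C: blinded challenges are marked at Visit 2 and one month after OIT cessation, with none marked at one year from trial start.

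If a one-year challenge in every patient is not already intended, it adds visits, mainly in the control arm.

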15 The impact of CMA: IgE mediated milk allergy is associated with a high frequency of unwanted reactions (12). In US surveys, it was ranked as second or third most common food requiring adrenalin treatment in children with food allergy (13, 14). This was due to the high frequency of dairy ingredients in common foods as well as medication and supplements (15, 16). Complete avoidance of dairy is thus difficult for families, and for the affected children and young adults.

The natural history of IgE mediated milk allergy is variable. It was reported that symptoms of CMA resolve for approximately 80% - 90% of children before the age of 5 (17). However, more recent studies indicate a later resolution of milk allergy and fewer children outgrowing CMA . In a study by Skripak et al, the median age for tolerance to cow's milk was 7 years \pm 11 months and at least 15% - 20% of their population retained their sensitivity into the second decade of life (18). This represents resolution at **older ages** than earlier studies (5). In addition, at least 20% of children who are diagnosed with CMA will have **life-long allergy** (5). The consequences of later resolution and prolonged allergy include important nutritional deficiency especially at critical times of bone growth and mineralization (19-21), in addition to the high risk of life-threatening events that accompany the increased exposures experienced by teens and young adults.

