3.0 Research Methods

3.1 Subject Selection: Eighty four boys and girls, between 6 to 20 years of age, diagnosed with IgE-mediated milk allergy, will be recruited for the study. Participants will be recruited from the allergy clinic at the Montreal Children's Hospital, Hopital Ste Justine, and the Centre de santé et de services sociaux de Chicoutimi.

Inclusion criteria: Children 6 years and older who satisfy **all** the following criteria will be included:

a. A **history** suggestive of IgE-mediated allergy to milk. An IgE-mediated reaction to a specific food is defined as a minimum of 2 mild symptoms and/or 1 moderate and/or 1 severe symptom that began within 1-20 minutes after ingestion or contact. Mild IgE-mediated symptoms include: pruritus, urticaria, flushing, or rhinoconjunctivitis. Moderate symptoms include angioedema (of face or lips), throat tightness, gastrointestinal complaints (vomiting, cramping, pain and/or diarrhea), or airway involvement (cough, nasal blockage, mucous); severe symptoms include bronchospasm, wheezing, hypoxia, cyanosis, low blood pressure, or circulatory collapse (shock) (appendix A ,table 1) (61).

b. The presence of **at least one** of the following confirmatory tests:

- (a) Positive skin prick test to milk (weal diameter 3 mm larger than that of the normal saline control). The allergen used will be commercially available milk extracts (Omega Labs, Montreal, QC). Skin tests will traced in ink, tape transferred to paper and wheal diameter measured by computer assisted planometry.
- (b) Detection of serum specific IgE (>0.35 kU/L) to milk or any of its proteins, measured by fluorescence enzyme immunoassay (Immunocap, Phadia, Uppsala, Sweden). The range for Immuncap is 0.35 – 100 and changes over time can be monitored effectively.

Following explanation of all facets of the protocol, informed consent and assent forms will be signed by the parents or legal guardian and subject, if applicable (Appendix B).

Exclusion criteria.

1. Patients with uncontrolled asthma or other uncontrolled respiratory diseases .
2. Malignancies, autoimmune diseases and/or severe primary or secondary immune deficiencies.
3. Patients receiving immunosuppressive therapy.
4. Patients receiving β -blockers (including topical formulations).
5. Associated diseases contraindicating the use of epinephrine: cardiovascular disease or severe hypertension.

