Through a process of stratified randomization (according to sex), participants will be randomly assigned to one of 2 study groups. The first group will receive active desensitization, and the second group will not receive any treatment but will be followed up regularly (Appendix A Table 2). Desensitization will be offered to the observation groups following the trial, should the outcome be successful in the treatment group.

3.2 Oral challenge test to milk. Prior to initiating desensitization and following treatment, the subjects will undergo a placebo controlled oral challenge to milk. These challenges will determine the level at which the children react and will be the baseline to follow their improvement in oral tolerance following therapy.

Oral challenges will be single blinded and will be performed with fresh cow's milk, with increasing doses taken orally every 10 to 15 minutes up to a total of 150ml of milk (doses of 0.1, 0.3, 1.0, 3.0, 10.0, 30.0, 45ml, 60 mL) ^{(49,82) (83)}. Patients will receive 2 challenges per day, 1 placebo and 1 with the active substance (milk). Nurses in the Medical Day Unit/Center for Investigative Medicine will prepare the food and randomize the placebo challenges. Unless contraindicated, the placebo will be soy or rice-based milk. If the challenge is negative after 150 ml of milk, results will be confirmed by means of open challenge, using 250ml of yogurt or ice cream 1 hour after completion of the blinded portion(29) according to the recommendations of the European Academy of Allergology and Clinical Immunology (5). After completing the challenge, patients will be kept under observation for at least 2 hours. Only objective symptoms will be considered to be indicative of a positive allergic reaction (29). Food challenges will be scored as positive if a single symptom or any of the following objective clinical reactions will be observed: urticaria, angioedema, wheezing, rhinitis, vomiting, diarrhea, protracted abdominal pain, exacerbation of atopic dermatitis, or shock. A single episode of vomiting will not be considered as a positive reaction, while severe and repetitive vomiting will. If the challenge is **negative**, ie, the subject is asymptomatic, he/she will be excluded from the study. Based on our experience, approximately 80% of those subjects ages 6 or greater, with positive history and positive skin tests, approached will fail the oral challenge and thus be eligible.

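### No between-arm comparison uses baseline age or the stratification factor sex, although age is a plausible predictor of spontaneous tolerance in a 6-to-20-year-old sample

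*Combined protocol and SAP*

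**What the plan says.** Section 3.1 sets the sample: "Eighty four boys and girls, between 6 to 20 years of age, diagnosed with IgE-mediated milk allergy, will be recruited for the study". The randomization paragraph that follows names one balancing factor: "Through a process of stratified randomization (according to sex), participants will be randomly assigned to one of 2 study groups". No reason is given for choosing sex.

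Section 4.0 B opens with "Statistical analyses will be performed using paired t-tests". For antibodies, skin tests and regulatory cells it adds that the values "will be compared with their baseline values using the one-sample paired t-test and to the control using a 2 sample t-test". Neither test carries a covariate. No between-arm test is named for the primary outcome in section 3.3.6, the three-category desensitization result at 1 year in which only total desensitization counts as success.

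Age and sex do appear in section 4.0 B, for a different purpose: "Multiple regression models will be used to assess factors associated with response to desensitization, including baseline demographic characteristics; gender; age". Treatment arm is not listed as a term in those models.

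On natural history, section 1.5 gives a median age at tolerance of 7 years in one cohort, says of the same cohort that "at least 15% - 20% of their population retained their sensitivity into the second decade of life", and cites a separate source for life-long allergy in at least 20%. Section 3.3.4 (Control Subjects) allows for controls who become tolerant without treatment.

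**The concern.** A control child who outgrows the allergy during the year can meet the primary endpoint untreated. If that is more likely at 6 or 7 than at 16, the expected control success rate depends on the age mix of the arm. Nothing in the randomization or the planned comparison deals with a chance difference in age mix between two arms of 42. Nor does the comparison use the factor on which randomization was stratified.

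At stake are the precision of the estimated treatment effect and how readily it can be defended. If the arms turn out to differ in age and no adjustment was pre-specified, any adjusted result will look post hoc.

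**Working it through.** The plan gives no figure for an age effect, so there is none to reproduce. The arm size of 42 is taken as given.

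**1. Implied remission rates.** Inputs from section 1.5: 50% still allergic at 7 (the median), and 15-20% still allergic in the second decade, at no stated age. Let S be the fraction still allergic at age A. The average annual remission from age 7 is 1 − (S/0.50)^(1/(A−7)).

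| Age A assumed for the 15-20% | S = 20% | S = 15% |
|---|---|---|
| 10 | 1 − 0.4^(1/3) = 26.3% | 1 − 0.3^(1/3) = 33.1% |
| 12 | 16.7% | 21.4% |
| 15 | 10.8% | 14.0% |
| 19 | 7.4% | 9.5% |

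The span is about 7% to 33%. Because the source figure is a minimum, each rate is an upper value for its age.

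**2. Do these figures require an age gradient?** A constant hazard of ln 2/7 = 0.099 per year is 9.4% annual remission at every age. It leaves 50% allergic at 7, 20% at about 16 and 15% at about 19, so it fits the median and the second-decade figure with no gradient. It would, however, keep falling below 20%, which conflicts with life-long allergy in at least 20%. Taken together, the three figures support remission that slows with age. They fix the direction, not the steepness.

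**3. Chance imbalance.** Assume half the children are younger. The SD of the between-arm difference in their share is √(2 × 0.25/42) = 0.109, with a 95% range of ±1.96 × 0.109 = ±21 points. If 30% are younger, the SD is √(2 × 0.21/42) = 0.100.

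**4. Effect on expected control success.** Let g be the gap in one-year remission between younger and older children. The control arm's expected untreated success, relative to what the treated arm would have shown untreated, shifts by imbalance × g. Older children are set at zero remission, so g equals the younger rate, which is its largest value:
- g = 0.074: 0.214 × 0.074 = ±1.6 points (95%)
- g = 0.12: ±2.6
- g = 0.20: ±4.3
- g = 0.26: ±5.6
- g = 0.33: ±7.1

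This passes in full to the estimated effect only if success on treatment has the same age gap. If it does not vary with age, only the control arm's own deviation counts: SD √(0.25/42) = 0.077, or about 0.71 of these values.

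**5. Error rate and power.** Simulation with 20,000 runs and 42 per arm. Half the children are younger with 30% remission, half older with 0%, and the gain is the same in both groups. A chi-square test ignoring age is set against a Mantel-Haenszel test stratified by age group.

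| True gain | Age ignored | Age-stratified test | Same test plus age-stratified randomization |
|---|---|---|---|
| 0 | 5.5% | 5.2% | not run |
| 25 points | 74.6% | 79.7% | 80.2% |
| 30 points | 87.4% | 91.0% | 91.6% |
| 50 points | 99.94% | 99.98% | 99.98% |

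With remission of 30%/5% and 12%/2%, the type I error ignoring age is 5.2% and 5.8%. The mean estimate matches the true difference to within 0.1 point in every scenario.

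**The case against.** The strongest objection is that section 1.5 reports cumulative figures only. No remission rate by age is stated, the second decade is not tied to an age, and the life-long figure comes from another source. Enrolled children must also fail an oral challenge (section 3.2), so cohort rates may not carry over to them. All of this stands. A reader might infer that age is a main driver of tolerance between 6 and 20. The documents support a plausible prognostic factor and no more.

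A second objection is that chance imbalance is already covered by the ordinary standard error. This also stands. A reader might infer that leaving age out biases the effect or inflates false positives. Randomization prevents the first, and the simulated type I error stays at about 5-6%.

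Third, age and sex are already planned covariates in section 4.0 B. They are, but in models of who responds, with no arm term listed, so those models do not adjust the treatment comparison.

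Fourth, the primary between-arm test is itself unnamed, which is the larger gap. That is true, and the adjustment is best written in when that test is defined.

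**Conclusion.** The gap is real and modest. No between-arm comparison uses baseline age or sex, and the protocol's own natural-history figures make age a plausible prognostic factor. The consequence is some lost precision and exposure to chance imbalance: an SD of about 11 points in the share of younger children, moving expected control success by roughly ±2 to ±7 points (95%). That range rests on half the children being younger and on no remission in older children; with a flat remission rate the shift would be zero.

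The loss of 4-5 points of power for a gain of 25-30 points uses 30% against 0% remission, near the steep end of what section 1.5 allows. For a 50-point gain nothing is lost. Section 4.0 A gives its expected 50% improvement without a scale, so the sponsor cannot assume the larger gain applies.

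A reader might also conclude that randomization must be re-stratified by age. The figures do not support that. Once the analysis is stratified by age, age-stratified randomization adds less than 1 point of power, and the documents supply no age cut.

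**What to change.** In section 4.0 B, name the between-arm analysis of total desensitization at 1 year and state in advance that it adjusts for baseline age and for the stratification factor sex. One form is a logistic regression on arm, age in years and sex, reported as a standardised risk difference with its confidence interval.

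Control successes may be few: expected control rates in the scenarios examined run from 3.6% to 17.5%, or about 1.5 to 7 of 42 children (42 × 0.036 and 42 × 0.175). The section should therefore name a fallback, such as a Mantel-Haenszel risk difference stratified by age group and sex, with the age cut fixed before outcomes are seen.

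This is a free improvement. Age and sex are already recorded for every child, so it needs one or two sentences in the plan and no new data, visits or change to the randomization list.
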